7.1.2. Planned Bayesian Statistical Analyses

Bayesian Statistical Analyses	
Endpoint(s)	
• $AUC[0-24]$	
• C_{max}	
Model Specification	
To guide dose selection after 3 doses in each part of the study have been observed, Bayesian posterior inferences about population probability distributions of model parameters of PK parameters will be assessed by using the following power model:	
$y = \exp(\theta_1 + r_i + \epsilon) \cdot dose^{\theta_2}$	
where y denotes the PK parameter being analyzed and r the random subject effect. The θ_s , $s=1,2$, in the power model will be estimated by linear regression of the \log_e -transformed PK parameters on \log_e dose levels.	
$\log(y_{ij}) = \theta_1 + \theta_2 \cdot \log(d_{ij}) + r_i + \epsilon_{ij} \quad (1)$	
where	

 y_{ij} is the observed or predicted PK variable of the j-th dose d_{ij} administered to the i-th subject. In particular, it is an $AUC[0-24]$ or a C_{max}, as applicable. θ_1, θ_2 are population intercept and slope, respectively. r_i is the random effect associated with subjects, it has mean zero and variance s^2 ϵ_{ij} is a random error term, with mean zero and variance σ^2. 	
Note, for part B, subjects will not receive more than one dose, therefore the random subject effect (r_i) will not be included in that model.	
In general, Bayesian inference seeks to quantify the probability distributions of model parameters such as the $(\theta_1, \theta_2, \sigma, s)$ defined in Equation (1). The present inference will	

Bayesian Statistical Analyses

incorporate a normal prior distribution, to express the prior information about the parameters (θ_1, θ_2) and a gamma prior distribution for (s^2, σ^2). Due to limited information available about the GSK3036656 compound, a non-informative prior with large variance will be used. For ease of parameterization for the normal distribution in computer programming, use $v = \sigma^{-2}$ and $w = s^{-2}$ as the precision. Model parameters are assumed *a priori* to be independent.

Table 3 Prior Distributions

Model Parameter	Prior
θ_1 (intercept)	\sim Normal (0, precision=0.001)*
θ_2 (slope of log-dose)	\sim Normal (0, precision=0.001)*
v (random error precision)	\sim Gamma (0.01, iscale=0.001)*
w (random effect precision)	\sim Gamma (0.01, iscale=0.001)*

All model parameters are *a priori* independent.

*SAS Version 9.3 or later or R version 3.1.1 or later will be used for the Bayesian analysis, specifying the normal distribution using mean and precision. At least two chains will be run for the estimation of each parameter.

Model Checking & Diagnostics

The posterior distributions of the model parameters will be estimated using the Markov Chain Monte Carlo (MCMC) method.

MCMC chains will be run for as many iterations as needed until convergence is achieved. Convergence will primarily be assessed using trace plots: All chains' trace plots will be inspected visually, to assess the mixing of each chain. Convergence is indicated when all chains appear to be mixing well and overlapping each other randomly (no chain's convergence is indicated until the chains of all model parameters appear well-mixed).

Additional convergence diagnostics, such as Monte Carlo Standard Error divided by the standard deviation of the posterior distribution (MCSE/SD), Gelman-Rubin statistic, effective sample size (ESS) and autocorrelation plots may also be reviewed.

The modelling will be subject to independent quality control, the final results for the probability of exceeding the pre-defined thresholds for both Cmax and AUC[0-24] should have a percentage of difference of $\leq 5\%$ to conclude agreement.

Model Results Presentation

Once the posterior distributions have been estimated, the following inferences and predictions will be estimated using the associated posteriors:

- Predictions of PK parameters AUC[0-24] and Cmax for potential future dose levels: mean, median, 5th and 95th percentiles.
- The Bayesian predictive probability that an individual subject will have AUC[0-24] or Cmax values greater than 4.9 $\mu\text{g.h/mL}$ and 0.443 $\mu\text{g/mL}$ (a 30-fold

Bayesian Statistical Analyses

margin from the dog no observed adverse effect level (NOAEL) exposure), respectively, will be calculated for each potential future dose level in Part 1 and Part 2. Note, prediction in Part 2 will be independent of Part 1.

- Graphical representation of the predictive distribution for AUC[0-24] and Cmax via line plots and density plots.

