6.3. Planned Dose Escalation and Adjustments

After the initial dose of GSK3036656, the decision to proceed to each subsequent dose level will be made by the Dose Escalation Committee (DEC) based on safety, tolerability and preliminary pharmacokinetic data from the prior lower dose level (Further details regarding dose escalation can be found in the 201040 Dose Escalation Charter). In Part A, safety data for at least 5 days post-dose and PK data for at least 2 days (48 hours) postdose from at least 4 subjects who received active treatment at the prior lower dose level will be reviewed before dose escalation. In Part B, safety data for at least the first 1 week (7 days) of dosing and PK data for at least the first 2 days (48 hours) of dosing from at least 4 subjects who received active treatment at the prior lower dose level will be reviewed before dose escalation. The actual doses to be administered will be selected by the DEC and may involve either an increase or a decrease in the dose, or repeating the same dose.

The exposures (AUC, Cmax) expected with the next selected dose will be predicted by pharmacokinetic assessment and modelling, and by calculating Bayesian predictive probabilities as data permit (more details in Section 10.3.1).

In toxicology studies in dogs, heart valvular and vascular lesions have been observed at relatively high doses and exposures; no such lesions have been seen in rats at similar exposures. To avoid the risk of this adverse event in the FTIH subjects, exposures in the FTIH study will be limited to predefined levels. Based on discussions with the GSK Cardiovascular Safety panel, the study will aim to limit the maximum individual daily plasma AUC(0-24) and Cmax after single or repeat dose to 4.9 µg.h/mL and 0.443 µg/ml, respectively - a 30-fold margin from the corresponding dog NOAEL exposures of 147.0 µg.h/mL and 13.3 µg/ml at which no valvular or vascular lesions have been detected.

Note: The term “mean” applied to group human exposure parameters (e.g., AUC) in this section refers to Geometric Mean of a dose cohort.

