6.3.1. Dose escalation in Part A

In Part A, bigger dose escalation steps may be allowed at lower doses and systemic exposures as the expected risk of adverse events at these exposures is low. At higher doses, smaller dose escalation steps will be used to minimize the risk of adverse events and gastrointestinal intolerance.

The following rules will guide dose selection in Part A:

1. No dose escalation to the next dose will be higher than 6-fold.
2. Once the dose is ≥ 300 mg, any further dose escalation will be no higher than 3-fold irrespective of the observed exposures.
3. The highest dose in Part A will not exceed 1500 mg.
4. A proposed dose will be acceptable if the predicted probability of an individual exceeding a Day 1 plasma AUC (0-24) of 4.9 µg.h/mL or Cmax of 0.443 µg/mL, as estimated by PK modeling and Bayesian analysis (if feasible), is no more than 10%.

5. Based on prior PK data, individual doses may be adjusted, if needed, such that a predicted individual Day 1 AUC (0-24) or Cmax does not exceed 4.9 $\mu\text{g.h/mL}$ or 0.443 $\mu\text{g/mL}$, respectively.

Dosing with food in Part A will be initiated after the exposures achieved with at least two dose levels administered in a fasted state are already known.

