6.3.2. Dose escalation in Part B

Part B may be initiated after the safety and PK data of at least three doses from Part A are already known. The decision to initiate Part B will be made by the GSK Study team in conjunction with the investigator.

The following rules will guide dose selection in Part B:

1. The starting daily dose in Part B will be selected such that its expected exposure (mean AUC[0-24] or Cmax) on the last day of dosing is no higher than the Day 1 exposure of a dose that has been found to be safe and well tolerated in Part A. The expected daily exposures during the dosing period, including on the last day of dosing, will be predicted based on the PK parameters for GSK3036656 established in Part A. As the highest exposure with repeat dosing is expected on the last day of dosing (as a result of accumulation), this approach would select a daily dose which provides systemic concentrations that, at any time during the period of dosing, are not likely to be higher than the ones already found to be safe and well tolerated in Part A.
2. Subsequent doses in Part B may be selected using the criteria described above for the starting dose in Part B. The expected daily exposures during the dosing period, including on the last day of dosing, will be predicted based on available PK data from Part A and from prior cohorts in Part B. Alternatively, a dose may also be selected even if it does not meet these criteria provided it is no more than 4-fold higher than a previous dose that has been found to be safe and well tolerated upon repeat dosing in Part B.
3. The highest daily dose in Part B will not exceed the highest single dose that has been found to be safe and well tolerated in Part A.
4. A proposed dose will be acceptable if the predicted probability of an individual exceeding a daily plasma AUC (0-24) of 4.9 $\mu\text{g.h/mL}$ or Cmax of 0.443 $\mu\text{g/mL}$ on any day of the dosing period, as estimated by PK modeling and Bayesian analysis (if feasible), is no more than 10%.

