10.11 Appendix 11: Example Mock Shells for Data Displays

Example : DE_T1
 Protocol : GSK3036656
 Population : Pharmacokinetic

Page 1 of n

Table DE_T1
 Summary of PK Parameters for Part A - Bayesian Prediction

PK Parameter Statistics	XX mg					
AUC[0-24] (µg.h/mL)						
N	X	X	X	NA	NA	NA
Observed Mean	X.XX	X.XX	X.XX	NA	NA	NA
Predictive Distribution						
Mean	X.XX	X.XX	X.XX	X.XX	X.XX	X.XX
5 th Percentile	X.XX	X.XX	X.XX	X.XX	X.XX	X.XX
Median	X.XX	X.XX	X.XX	X.XX	X.XX	X.XX
95 th Percentile	X.XX	X.XX	X.XX	X.XX	X.XX	X.XX
Cmax (µg/mL)						
N	X	X	X	NA	NA	NA
Observed Mean	X.XX	X.XX	X.XX	NA	NA	NA
Predictive Distribution						
Mean	X.XX	X.XX	X.XX	X.XX	X.XX	X.XX
5 th Percentile	X.XX	X.XX	X.XX	X.XX	X.XX	X.XX
Median	X.XX	X.XX	X.XX	X.XX	X.XX	X.XX
95 th Percentile	X.XX	X.XX	X.XX	X.XX	X.XX	X.XX

Example : DE_T2
Protocol : GSK3036656
Population : Pharmacokinetic

Page 2 of n

[figure not shown]
Table DE_T2
Summary of PK Parameters for Part A - Bayesian Predictive Probability of Exceeding Threshold

PK Parameter	Threshold	Probability (greater than threshold observed data)					
		XX mg	XX mg	XX mg	XX mg	XX mg	XX mg
AUC [0-24] (µg.h/mL)	4.9	0.XX	0.XX	0.XX	0.XX	0.XX	0.XX
Cmax (µg/mL)	0.443	0.XX	0.XX	0.XX	0.XX	0.XX	0.XX

Example : DE_F1
Protocol : GSK3036656
Population : Pharmacokinetic

Page 3 of n

[figure not shown]
Table DE_F1
Dose Response Curve of Predictive Distributions for AUC[0-24] Part A

Example : DE_F2
Protocol : GSK3036656
Population : Pharmacokinetic

Page 4 of n

Table DE_F2
Density Plot of Predictive Distributions for AUC[0-24] Part A

Example : PK_T1
Protocol : GSK3036656
Population : Pharmacokinetic

Page 5 of n

Table PK_T1
Statistical Analysis of log transformed plasma GSK3036656 Pharmacokinetic Parameters Assessing Dose Proportionality (Power Model)
Part A / Part B

Parameter (units)	Slope Log Parameter vs Log Dose	90% CI of the Slope
AUC(0-t) (μg.h/mL)	x.xx	(x.xxx, x.xxx)
AUC(0-∞) (μg.h/mL)	x.xx	(x.xxx, x.xxx)
AUC(0-τ) (μg.h/mL)	x.xx	(x.xxx, x.xxx)
Cmax (μg/mL)	x.xx	(x.xxx, x.xxx)

Example : PK_T2
 Protocol : GSK3036656
 Population : Pharmacokinetic

Page 6 of n

Table PK_T2
 Statistical Analysis of log transformed plasma GSK3036656 Pharmacokinetic Parameters Assessing Food Effect Part A

Parameter (units)	Treatment	Comparison	Geom.LsMean				Ratio	90% Confidence Interval
			n	Test	n	Ref		
AUC (0-t) (µg.h/mL)	XXmg	Fed vs Fasted	xx	x.xxx	xx	x.xxx	x.xxx	(x.xxx, x.xxx)
AUC (0-∞) (µg.h/mL)	XXmg	Fed vs Fasted	xx	x.xxx	xx	x.xxx	x.xxx	(x.xxx, x.xxx)

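### The protocol caps the predicted chance of an individual exceeding the AUC(0-24) or the Cmax limit at 10%, but the SAP reports one chance per measure and never computes the either-limit chance

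*SAP*

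**What the plan says.** Protocol 6.3.1, rule 4 (Part A): "A proposed dose will be acceptable if the predicted probability of an individual exceeding a Day 1 plasma AUC (0-24) of 4.9" µg.h/mL or a Cmax of 0.443 µg/mL, "as estimated by PK modeling and Bayesian analysis (if feasible), is no more than 10" per cent.

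Protocol 6.3.2, rule 4 (Part B), has the same structure, but the event may occur "on any day of the dosing period, as estimated by PK modeling and Bayesian analysis (if feasible), is no more than 10" per cent.

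Protocol 10.3.1 likewise describes a single Bayesian predictive probability of an individual exceeding one limit or the other. Escalation stopping criterion 2 (Protocol 5.5) is met when one subject exceeds either limit.

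SAP 7.1.2 fits the power model to AUC[0-24] or to Cmax, as applicable. It has a subject effect (Part A only) and a residual, and no term linking the two measures. The output is "The Bayesian predictive probability that an individual subject will have AUC[0-24] or Cmax values greater than" 4.9 µg.h/mL and 0.443 µg/mL, respectively. The mock table DE_T2 in SAP Appendix 11 ("Bayesian Predictive Probability of Exceeding Threshold") has one row for AUC[0-24], one for Cmax and none for either. The SAP does not restate the 10% or say how the two rows are to be set against it. Its list of changes from the protocol (SAP 2.1) declares only the added random effect.

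**The concern.** The rule caps the probability of a union of two events. The SAP delivers the two component probabilities and nothing that joins them. A Dose Escalation Committee that reads DE_T2 and finds each row at or below 10% could conclude that rule 4 is met when the probability the rule describes is above 10%.

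The exposure limits were set because of valvular and vascular lesions in dogs, and Protocol 4.6.1 describes that pathology as not monitorable in humans. The predicted chance of exceeding a limit is one of the safeguards meant to prevent such exposure, so it should be computed as the protocol defines it.

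**Working it through.** **Inputs.** Cap: 10% (Protocol 6.3.1 and 6.3.2, rule 4). Limits: AUC(0-24) 4.9 µg.h/mL and Cmax 0.443 µg/mL, described in Protocol 6.3 as "a 30-fold margin from the corresponding dog NOAEL exposures of 147.0" µg.h/mL and 13.3 µg/mL. The AUC–Cmax correlation rho on the log scale is not in the documents, so I assume a range of 0.5 to 0.95.

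**The plan's own figures.** 147.0/30 = 4.90 and 13.3/30 = 0.4433, so both limits reproduce. The documents state no either-limit probability to reproduce.

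**Formula.** Let p1 = P(AUC(0-24) > 4.9) and p2 = P(Cmax > 0.443) for an individual.

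P(either) = p1 + p2 − P(both)

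P(both) is the upper-tail probability of a standard bivariate normal with correlation rho beyond z(1−p1) and z(1−p2). It cannot exceed the smaller of p1 and p2, so P(either) is never below the larger row. It equals the larger row only when exceeding one limit implies exceeding the other.

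**Both rows at the cap.** z(0.90) = 1.2816.
- rho 0.95: 0.10 + 0.10 − 0.0779 = 12.2%
- rho 0.9: 0.20 − 0.0689 = 13.1%
- rho 0.7: 0.20 − 0.0468 = 15.3%
- rho 0.5: 0.20 − 0.0324 = 16.8%

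At rho = 0 it is 19.0%; at rho = 1 it is 10%. A t-shaped predictive distribution with 5 to 16 degrees of freedom changes little: 12.0–12.2% at rho 0.95 and 16.2–16.6% at rho 0.5.

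**Varying the second row.**

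| Rows | rho 0.95 | rho 0.9 | rho 0.7 | rho 0.5 |
|---|---|---|---|---|
| 10% and 10% | 12.2% | 13.1% | 15.3% | 16.8% |
| 10% and 5% | 10.3% | 10.7% | 12.1% | 13.1% |
| 10% and 2% | 10.0% | 10.1% | 10.6% | 11.1% |
| 10% and 1% | 10.0% | 10.0% | 10.2% | 10.5% |
| 8% and 8% | 9.9% | 10.6% | 12.5% | 13.6% |

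The last line shows that two rows below the cap can still give more than 10%. For equal rows, P(either) stays at 10% only if each row is at most 8.1% (rho 0.95), 7.5% (0.9), 6.3% (0.7) or 5.7% (0.5).

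**Which limit is likely to bind?** The limits imply an AUC/Cmax ratio of 4.9/0.443 = 11.1 h. For illustration I assume one compartment and instantaneous absorption, so AUC(0-24)/Cmax = (1 − exp(−24k))/k.
- From the predicted half-life (Protocol 4.1), k = ln 2/half-life. The ratio is 13.0 h at 12 h, 18.4 h at 30 h and 21.4 h at 72 h, all above 11.1 h, so AUC binds first.
- From the predicted clearance and volume (Protocol 4.5), k = CL/V. With 7.2 mL/min/kg and 3.5 L/kg, k = 0.432/3.5 = 0.123 per hour and the ratio is 7.7 h. With 1.1 mL/min/kg and 4.5 L/kg, k = 0.066/4.5 = 0.0147 per hour and the ratio is 20.2 h. These lie on both sides of 11.1 h.

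Next I set AUC at 10% and take the 50% CV for clearance (Protocol 4.5) as the spread of both measures. The log-scale SD is sqrt(ln 1.25) = 0.472. At a 30 h half-life the Cmax limit lies at z = 1.2816 + ln(0.443 × 18.4/4.9)/0.472 = 2.36, so p2 = 0.9% and P(either) is 10.0–10.4% for rho 0.95–0.5. At 12 h it is 10.3–13.2%; at 72 h it is 10.0–10.2%.

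**The case against.** **The rule may mean 10% per measure.** The word 'respectively' in SAP 7.1.2 and the two-row layout of DE_T2 fit that reading, and the Dose Escalation Charter that Protocol 6.3 points to is not available here. This stands as a possibility, but neither document says it. Rule 4 and Protocol 10.3.1 each speak of one probability joined by 'or'. Stopping criterion 2 concerns observed rather than predicted exposure, so it does not settle how the prediction is calculated, but it is triggered by the same either-limit event.

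**The excess may be negligible.** At the average predicted half-life the AUC limit dominates and the either-limit risk is barely above 10%. This largely stands as a point about size. It is not proof that the gap is harmless: it rests on a one-compartment approximation, a marked distribution phase would lower the AUC/Cmax ratio, and the predicted clearance and volume ranges allow either limit to bind.

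**Other controls exist.** A reader might infer that the 10% figure is the main quantitative safety gate. The documents do not support that. The probability is used alongside safety and tolerability data to aid selection, and the Bayesian analysis applies if feasible. Step-size caps, individual dose adjustment in Part A, the Part B dose rules, committee review and stopping after a single exceedance all operate separately.

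**Population PK simulation could supply the joint figure.** SAP 7.1.3 simulates individuals against both margins, and one simulated profile yields both measures. This is a partial answer: the SAP places that modelling at the first two dose levels and promises no either-limit output.

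**Conclusion.** The gap is real. On the literal reading of rule 4, following SAP 7.1.2 and DE_T2 does not produce the probability that the protocol caps, and the SAP does not declare the change.

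Two stronger readings should be resisted. A reader might infer that doses passing both rows will typically carry a 12–17% risk. That range needs both rows at 10% and a correlation of 0.5 to 0.95, which is near a worst case for those correlations. A reader might also infer that the larger row always understates the risk. It can never overstate it and usually understates it, but the difference vanishes when exceeding one limit implies exceeding the other.

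The size therefore rests on two unknowns, the correlation and the second row, and runs from almost nothing when one limit dominates to about 7 percentage points when both bind at rho 0.5. It also assumes approximate bivariate normality on the log scale. The point concerns the Bayesian step used once three dose levels are available. It merits correction before that step is used, in proportion to a modest but avoidable mismatch.

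**What to change.** Reconcile the SAP with rule 4:

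1. Add a row to DE_T2 for P(AUC(0-24) > 4.9 µg.h/mL or Cmax > 0.443 µg/mL) for an individual, and state in SAP 7.1.2 that this row is compared with the protocol's existing 10%.
2. Obtain it from a bivariate version of the power model (correlated residuals and, in Part A, correlated subject effects), or by counting either-limit exceedances in the population PK simulations of SAP 7.1.3.
3. If neither is feasible, use p1 + p2 as a conservative bound. It needs no new modelling and no correlation.
4. If the sponsor intends 10% per measure, state that in both the protocol and the SAP, and still show the either-limit probability.

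**Cost.** One table row and slightly more modelling. With about six active subjects per dose in Part A and vague priors, the correlation will be poorly estimated, so the bound in step 3 is a useful cross-check. Some doses will look slightly less acceptable, and the bound is strict when the measures are highly correlated: two rows of 8% sum to 16%, against 9.9% at rho 0.95.

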5.5. Dose Escalation Stopping Criteria

Dose escalation in Part A or Part B will be stopped if any of the following occurs in a group/cohort:

1. There is substantially increased incidence and/or severity of clinically significant adverse events or withdrawals possibly related to GSK3036656 in the active treatment subgroup at the last dose level administered as compared to the placebo subgroup. The GSK Study Team in conjunction with the study investigator will determine the significance of the adverse events or withdrawals and make a decision about whether stopping further dose escalation is necessary.
2. At least one subject has a plasma AUC (0-24) higher than 4.9 µg.h/mL or a plasma Cmax higher than 0.443 µg/mL on any day.
3. For Part A, no meaningful increase in exposure is observed with increase in dose (i.e., a plateau in exposures is reached).

Note: If dose escalation is stopped due to reasons 1 or 2 above occurring at the last dose, dosing at a lower level (e.g., an intermediate level between the last dose and a previous dose where dose escalation stopping criteria were not met) could be allowed. The GSK Study Team in conjunction with the study investigator will decide whether dosing at such level could be done and will select the dose to be administered.

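### Does the SAP's Part B exceedance probability fail the protocol's any-day rule because it names no day?

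*SAP*

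**What the plan says.** The protocol sets the day separately for each part. For Part A, section 6.3.1 rule 4 begins "A proposed dose will be acceptable if the predicted probability of an individual exceeding a Day 1 plasma AUC (0-24"), and its ceiling of 10% covers both the AUC and the Cmax limit. For Part B, section 6.3.2 rule 4 applies the same 10% to exceedance "on any day of the dosing period, as estimated by PK modeling and Bayesian analysis", where feasible. Rule 1 explains which day matters: "As the highest exposure with repeat dosing is expected on the last day of dosing (as a result of accumulation"). Rule 2 says that expected daily exposures, including the last day's, "will be predicted based on available PK data from Part A and from prior cohorts in Part B". It then adds a second route: "Alternatively, a dose may also be selected even if it does not meet these criteria provided it is no more than 4-fold higher". The comparison there is with an earlier Part B dose already judged safe and tolerable. Rule 3 takes its ceiling from the Part A results: "The highest daily dose in Part B will not exceed the highest single dose that has been found to be safe and well tolerated". Section 5.5 stops escalation if "At least one subject has a plasma AUC (0-24) higher than 4.9" µg.h/mL, or a Cmax above 0.443 µg/mL, on any day.

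SAP 7.1.2 fits a power model to AUC(0-24) or Cmax after three doses in each part. It keeps the Part B prediction independent of Part A, and the individual exceedance probability "will be calculated for each potential future dose level in Part 1 and Part 2" (read as Parts A and B). No day appears there or in shells DE_T1, DE_T2, DE_F1 and DE_F2, which are reused for Part B. SAP 7.1.3 describes a population PK model, if feasible, and a simulation of the probability that an individual exceeds the exposure margins. It names neither a part nor a day.

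**The concern.** Part B has full PK profiles on both Day 1 and Day 14, so a response called only AUC(0-24) could be taken from either. If the drug accumulates, the two days give very different probabilities against the same 10% limit. The limits exist because of dog heart valve and vascular lesions that protocol 4.6.1 calls not monitorable in humans, so a probability for the wrong day would matter.

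Two features sharpen the worry. The power model needs three earlier Part B doses and there are at most four cohorts, so it can inform only the fourth. For the first three, the only planned source of a probability is the simulation in SAP 7.1.3, which is not tied to Part B. In addition, the second route in rule 2 drops the last-day limit on mean exposure. On that route rule 4 may be the only probability check made in advance, since section 5.5 acts after an excess has occurred.

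**Working it through.** **The plan's own figures.** The limits are the dog NOAEL exposures divided by 30: 147.0/30 = 4.90 µg.h/mL and 13.3/30 = 0.443 µg/mL. Both reproduce.

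**How far the power model reaches.** With at most four Part B doses and three needed first, it can inform dose 4 only, and none if fewer than four dose levels are run.

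**How much the day could matter.** Inputs: half-life about 30 h, range 12 to 72 h (protocol 4.1); 50% CV (protocol 4.5, where it is the assumption for clearance). I assume linear one-compartment kinetics, once-daily dosing and log-normal exposure.

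- Log-scale SD: σ = √ln(1.25) = 0.472.
- With q = 2^(−24/t½), the Day 14 to Day 1 AUC(0-24) ratio is R = (1 − q^14)/(1 − q).
- For a dose with exactly 10% exceedance on Day 1, the geometric mean that day is 4.9 × exp(−1.2816 × 0.472) = 2.67 µg.h/mL.
- Its Day 14 exceedance is 1 − Φ(1.2816 − ln R/σ).

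| Half-life | R | Day 14 geometric mean (µg.h/mL) | Day 14 exceedance |
|---|---|---|---|
| 12 h | 1.33 | 3.57 | 25% |
| 30 h | 2.35 | 6.28 | 70% |
| 72 h | 4.66 | 12.5 | 98% |

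So the choice of day is material if it is made wrongly.

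**What it would take to make it wrongly.** All of these must hold together:

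1. Day 1 values are modelled or simulated for Part B.
2. The resulting probability is used for rule 4, although that rule says any day and rule 1 says the peak is on the last day.
3. The dose is chosen by the second route in rule 2. On the main route, last-day mean exposure is held to the Day 1 exposure of a Part A dose found safe. If that Part A dose met the 10% rule, Day 14 exceedance is held near 10% or less.
4. The dose lies right at the 10% boundary.
5. The stopping criterion in section 5.5 has not already halted escalation.

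**Credit for the stopping criterion.** Take the dose in the table and suppose the preceding Part B dose was f-fold lower, with 8 active subjects and Day 14 data complete. Its Day 14 geometric mean is the table value divided by f, its individual exceedance is p = 1 − Φ(ln(4.9/mean)/σ), and the chance that escalation has already stopped is 1 − (1 − p)^8.

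- 72 h, f = 4: mean 12.45/4 = 3.11, p = 17%, chance 77%. With f = 3: p = 36%, chance 97%.
- 30 h, f = 2: mean 6.28/2 = 3.14, p = 17%, chance 78%. With f = 4: p = 0.8%, chance 6%.

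Once those data are in, the extreme figure of 98% is therefore not a likely fourth-dose situation. The protection is weak at 30 h with a 4-fold step, or where the earlier cohort has not finished.

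**Would naming Day 14 settle it?** Not fully, for two reasons.

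- *Timing.* With cohort starts s days apart, the fourth decision falls on day 3s and the third cohort's Day 14 AUC(0-24) is complete on day 2s + 14. Day 14 data from three doses exist only if s ≥ 14. At s = 7 the three cohorts complete on days 14, 21 and 28, against a decision on day 21. Selection would then return to the simulation already in SAP 7.1.3.
- *Meaning.* Day 14 is not the maximum over days once exposure varies within a subject. I simulated independent day-to-day variation with log SD 0.15 to 0.25, keeping total CV at 50%. A dose with 10% exceedance on Day 14 then has about 20% to 30% on at least one day at a 30 h half-life, and about 17% to 24% at 72 h. A Day 14 label would still fall short of the any-day wording.

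**The case for a change.** The strongest case for a change is that a statistical plan should define what it estimates. The protocol names Day 1 for Part A and any day for Part B, while the SAP names nothing, so two careful analysts could report different probabilities against one threshold. The qualifier on feasibility in rule 4 excuses an analysis that cannot be done, not one left undefined. If population PK is infeasible, the stated fallback of dose proportionality yields no probability at all. Escalation may also proceed on 48 hours of PK data. These reach only Day 2, when AUC(0-24) is 94%, 67% or 39% of its Day 14 value at the three half-lives.

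The omission itself stands. The inference that the rule goes unserved does not. The SAP need not repeat an acceptance rule that the protocol states in full, and protocol 4.5 and 6.3 define the limits as maximum individual daily exposure after single or repeat dosing. The exposure margins in SAP 7.1.3 can be read with that meaning. Its population PK model is not barred from combining Part A and Part B data, because the independence note concerns the power model. Infeasibility is also unlikely by then: Part B may start only after data from at least three Part A doses, with up to six active subjects each sampled to 72 hours. Protocol 6.3 places further escalation detail in a Dose Escalation Charter, which is not among the documents and may name the day.

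**Conclusion.** No change to the plan follows. SAP 7.1.1 to 7.1.3 and the dose-escalation shells leave out the day for Part B, but this is missing detail and not a conflict with the protocol. The protocol supplies the any-day criterion, the expected day of the peak and the data to be used, so a competent analyst fills the gap in the intended way. The 25%, 70% and 98% figures show what a Day 1 reading would cost under linear kinetics and 50% CV for AUC; Cmax was not quantified. They do not describe what the plan would do, because they need several conditions at once, including a reading that departs from rule 4. A Day 14 label would add little: it would often lack data at the fourth decision and would still not equal any-day exceedance. The conclusion assumes that rule 4 is applied as written and that the simulation in SAP 7.1.3 is run for Part B where feasible. It makes no judgement on the escalation rules themselves.
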